## 10.18 Medications Assessment

The name, dose, frequency and route of all medications will be collected at all visits. Changes to medications will be captured on the Medication Log eCRF.

There are no medications that are required for this study although some medications may be administered in treating specific conditions at the discretion of the physician. The only medications that are excluded from use during this study are investigational.

## 10.19 Assessment of Safety

All LINQ™ system and procedure related adverse events (AEs), all serious adverse events (SAEs), all Pulmonary related AEs and all Cardiovascular related AEs will be collected throughout the duration of a subject's participation in the study, beginning at the time of informed consent. Additionally, any device deficiencies related to the LINQ™ system will be collected. Adverse events and device deficiencies will be reported to Medtronic via completion of eCRFs. See section 12.0 for additional details.

LINQ™ system and procedure related AEs reported in the study will be summarized as an ancillary objective. Additionally, reported device deficiencies will be summarized.

## 10.20 Review of Data Recorded by the Reveal LINQ™ Device

Reveal LINQ™ data derived from the investigational RAMware will not be viewable to the site. The standard arrhythmia data from the LINQ™ device will be viewable via CareLink.

## 10.21 Recording Data

Subject data will be collected on electronic case report forms (eCRFs) via a web-based remote data capture (RDC) system. The investigator must ensure accuracy, completeness and timeliness of the data

reported in the eCRFs. Only authorized persons can complete and sign e-CRFs, as specified on the Delegated Tasks List included in the Investigator Site File.

Procedures in the CIP require source documentation. Source documents, which may include worksheets and subject medical records, must be created and maintained by the investigational site team. Subject records must be clearly marked to indicate that subject participates in the study. When copies or printouts of source documents are made, these must be signed and dated by a member of the investigational site team with a statement that it is a true reproduction of the original source document.

Device data from transmissions will be uploaded to secure servers. Media/USB data collected at office visits will be sent to Medtronic. Upon receipt, device data will be maintained with databases and retrieved for analysis and reporting.

Refer to section 16.2 for additional detail regarding data management for the study.

## 10.22 Deviation Handling

A study deviation is defined as an event within a study that did not occur according to the Clinical Investigation Plan or the Clinical Trial Agreement. If an infringement remains unresolved, multiple deviations need not be completed.

Prior approval by Medtronic is expected in situations where the investigator anticipates, contemplates, or makes a conscious decision to deviate. Prior approval is not required when a deviation is necessary to protect the safety, right or well-being of a subject in an emergency or in unforeseen situations beyond the investigator's control (e.g. subject failure to attend scheduled follow-up visits, inadvertent loss of data due to computer malfunction, inability to perform required procedures due to subject illness).

For medically justifiable conditions which preempt a subject's ability to complete a study-required procedure, it may be permitted to report only one deviation which will apply to all visits going forward. This may also apply for other unforeseen situations (e.g. the subject permanently refuses to complete a study required procedure and the data will not contribute to the primary end point analysis). However, prior approval from Medtronic is required for such situations.

All study deviations must be reported on the study deviation e-CRF regardless of whether medically justifiable, pre-approved by Medtronic, an inadvertent occurrence, or taken to protect the subject in an emergency. The deviation description and reason for deviation must be recorded. Multiple deviations of the same type at the same visit may be reported on one e-CRF.

In the event the deviation involves a failure to obtain a subject's consent or is made to protect the life or physical well-being of a subject in an emergency, the deviation must be reported to the IRB/EC as well as Medtronic within five (5) working days. Reporting of all other study deviations must comply with IRB/EC policies and/or local laws and/or regulatory agency requirements and must be reported to Medtronic as soon as possible upon the center becoming aware of the deviation. Refer to Table 12 for geography

specific deviation reporting requirements and timeframes for reporting to Medtronic and/or regulatory bodies.

Medtronic is responsible for analyzing deviations, assessing their significance, and identifying any additional corrective and/or preventive actions (e.g. amend the Clinical Investigation Plan, conduct additional training, terminate the investigation). Repetitive or serious investigator compliance issues may result in initiation of a corrective action plan with the investigator and site, and in some cases, necessitate suspending enrollment until the problem is resolved or ultimately terminating the investigator's participation in the study. Medtronic will provide site-specific reports to investigators summarizing information on deviations that occurred at the investigational site on a periodic basis.

## 10.23 Subject Exit, Withdrawal or Discontinuation

### 10.23.1 Study Exit

Study exit is defined as the moment when a subject officially stops participating in the study. Subjects will be considered exited upon completion of the study exit e-CRF. Prior to exiting a subject from the study, it is recommended to follow the subject until any ongoing AEs related to the Reveal LINQ™ system or procedure are classified by the investigator, as resolved. The date and reason for subject exit must be reported to Medtronic at the earliest opportunity via eCRF. Exited subjects will not be replaced. Upon exiting from the study, no further study data will be collected, or study visits will occur for the subject. All data available through the time of the subject's exit will be used for analysis. Subjects are urged to remain in the study as long as possible but may be exited from the study for any of the following situations:

- Subject did not meet inclusion/exclusion criteria and was not inserted with a LINQ™ device
- LINQ™ ICM explanted and not replaced with a new LINQ™ ICM (e.g. diagnosis determined, suspected infection, subject request, physician determination)
- Subject chooses to withdraw (e.g., consent withdrawal, relocation to another geographic location)
- Investigator chooses to withdraw a subject (e.g., medically justified, inclusion/exclusion criteria not met, failure of subject to maintain adequate study compliance)
- Implant attempted, however no Reveal LINQ™ was implanted
- Subject lost to follow-up
- Death
- Study completion or termination

The following information/procedure is to be collected/Performed at study exit:

- Date of exit
- Reason for exit
- Medications Assessment
- St. George's Respiratory Questionnaire

- Laboratory results: Creatinine, Brain natriuretic peptide (BNP) OR N-terminal brain natriuretic peptide (NT-proBNP), White blood cells, Eosinophils
- Initial Device Interrogation (save to media via USB) (prior to removal)
- Removal of the investigational RAMware from the LINQ™ device
- Opting out of the subject diary
- Post Device interrogation (save to media via USB) (post removal)
- Adverse events
- Device deficiencies
- Study deviations

## 10.23.2 Study Completed

All subjects will be exited from the study when the last subject's 6-month follow-up visit is completed or until official study closure, defined as when Medtronic and/or regulatory requirements have been satisfied per the Clinical Investigation Plan and/or by a decision by Medtronic or regulatory authority, whichever occurs first. Subjects will be provided standard medical care by their physician after their study participation ends.

## 10.23.3 Lost to Follow-up

In the case that the subject is determined to be lost to follow-up, details of a minimum of two attempts and the method of attempt (e.g., one letter and one phone record or two letters) to contact the subject must be recorded. In addition, follow the regulations set forth by the governing IRB/EC.

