### **9.3 Inclusion Criteria**

- Patient is  $\geq$  45 years old
- Patient (or patient's legally authorized representative) is willing and able to provide written informed consent
- Patient is willing and able to comply with the protocol, including follow-up visits, diary submissions and CareLink transmissions
- $\text{FEV}_1$  (post bronchodilator)  $\leq$  70% of predicted
- Current or former smoker with lifetime cigarette consumption of  $\geq$  10 pack-years

- One COPD exacerbation in the previous 12 months requiring hospitalization, urgent care or emergency department visit for respiratory illness OR Two COPD exacerbations within the previous 12 months requiring antibiotics and/or corticosteroids for respiratory symptoms
- The patient's medical records must be accessible by the enrolling site over the follow-up period

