## 12.6 Subject Death

All subject deaths must be reported by the investigator to Medtronic on an AE form (AE with fatal outcome) as soon as possible after the investigator first learns of the death. In case of death, there should be one AE CRF with an outcome of fatal.

In the event of a subject's death, the inserted system should be explanted and returned to Medtronic for analysis whenever possible. Local laws and procedures must be followed where applicable. If any device or system component is returned to Medtronic, internal returned product reporting systems may be used to gather additional information about the returned device/component.

A copy of the death certificate, if available and allowed by state/local law, should be sent to the Medtronic clinical study team. When a death occurs in a hospital, a copy of the death summary report and all relevant hospital records should be sent to the Medtronic clinical study team, if available. If an autopsy is conducted, the autopsy report should also be sent to the Medtronic clinical study team if available and allowed by state/local law. When the death occurs at a remote site, it is the investigative site's responsibility to attempt retrieval of information about the death. Additionally, device disposition information should be updated. In summary, the following data will be collected:

- Date of death
- Detailed description of death
- Cause of death
- Relatedness to system and/or procedure
- Device interrogation (if available, postmortem preferred)
- Death summary/hospital records (if available and allowed by state/local law)
- Autopsy report (if available and allowed by state/local law)
- Death certificate (if available and/or allowed by state/local law)

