7.9.3 Analysis Methods

Data from multiple study components will be collected in this study, of which the Reveal LINQ™ HF derived data is of the most interest. This includes subcutaneous electrocardiogram, impedance, temperature, accelerometer and patient activity measurements.

Descriptive statistics such as mean and standard deviation for continuous variables and count and proportion for categorical variables will be used to summarize the derived data from Reveal LINQ™ HF. The relationship between changes in LINQ™ derived data and COPD events per EAC adjudication will be evaluated. Specifically, for each subject that has experienced at least one COPD event per EAC adjudication, the average daily measurements of LINQ™ derived data before and after a COPD event will be plotted to identify patterns and signals related to the occurrence of the COPD event.

In addition, exploratory survival analyses for time to first COPD event through 12-months of follow-up such as a Kaplan-Meier curve and Cox proportional hazards regression models with independent variables such as demographics and comorbidities will be included.

Each subject's time to first detected and adjudicated COPD event will be defined as the time from insertion date to the onset date of first COPD event. Subjects who have not experienced a COPD event through 12 months will be censored at:

- (1) their point of last contact, usable Reveal LINQ ICM interrogation or CareLink transmission if they occur before or at 12 months, whichever is later

or

- (2) 12 months (374 days) if their point of last contact, usable Reveal LINQ ICM interrogation or CareLink transmission go beyond 12 months.

Survival estimates and hazard rate with 95% confidence intervals will be reported.

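### A subject can be exited as lost to follow-up without a check of the medical record, and the SAP's censoring date can then fall after the last date on which anyone asked about COPD events

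*Protocol*

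**What the plan says.** **Loss to follow-up.** CIP 10.23.3 asks the site to record "details of a minimum of two attempts and the method of attempt (e.g., one letter and one phone record or two letters"). The only other instruction is "In addition, follow the regulations set forth by the governing IRB/EC". The section sets no interval between attempts and asks for no review of records or vital status.

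**Record access.** An inclusion criterion in CIP 9.3 reads "The patient's medical records must be accessible by the enrolling site over the follow-up period".

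**Event capture.** CIP 10.10 says the diary will not be screened for reportable adverse events, because these are formally collected at scheduled follow-up. Under CIP 10.12.1 that means a telephone call every three months.

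**After exit.** CIP 10.23.1 states: "Upon exiting from the study, no further study data will be collected, or study visits will occur for the subject". It also states: "All data available through the time of the subject's exit will be used for analysis".

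**Deaths.** CIP 12.6 states: "All subject deaths must be reported by the investigator to Medtronic on an AE form". The duty runs from when the investigator learns of the death.

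**Censoring.** SAP 7.9.3 states: "Subjects who have not experienced a COPD event through 12 months will be censored at" the latest of last contact, last usable device interrogation and last CareLink transmission, capped at 374 days. It does not separate manual transmissions from the automatic nightly ones that CIP 10.11 sets up.

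**The concern.** A subject who does not answer a call or a letter may be silent because of the outcome under study: admitted, in post-acute care, or dead. The CIP's own background (4.1) makes this plausible. After an admission for exacerbation, it reports that about 11% die and 35% are readmitted within 90 days.

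For such a subject the three-monthly call is the main route by which events reach the sponsor, and that route has failed. Sites cannot see the RAMware data (CIP 10.20). The medical record is the obvious backstop, and access to it is already secured, but 10.23.3 does not use it.

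Two things are at stake. First, the set of adjudicated COPD events may be incomplete in a way related to severity. Second, the Kaplan-Meier and Cox analyses assume that censoring is unrelated to the event. That assumption weakens if loss is driven by events. Separately, if an automatic transmission sets the censoring date, the subject contributes event-free time over a period when nobody was ascertaining events.

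**Working it through.** **1. The plan's own figure.** Inputs from CIP 14.4 and SAP section 6: 60 subjects, 12 months, 2 exacerbations per patient-year, 50% meeting the COPD event definition.

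- Exacerbations: 60 × 2 × 1 = 120.
- COPD events: 120 × 0.5 = 60, or 1 per patient-year.

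Both stated figures reproduce. Neither allows for loss.

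**2. Events hidden behind loss.** The documents give neither a loss rate nor the share of losses that conceal an event. Assumed: 5–15% lost, 25–50% of those hiding one COPD event.

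- Lost: 60 × 0.05 = 3 to 60 × 0.15 = 9 subjects.
- Hidden events: 3 × 0.25 = 0.75 to 9 × 0.50 = 4.5.
- Share of 60 expected: 0.75/60 = 1.25% to 4.5/60 = 7.5%.

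This is an upper figure. It treats every hidden admission or death as an adjudicated COPD event and assumes that no existing reporting route catches any of them.

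**3. Effect on the 12-month first-event estimate.** Assume a constant rate of 1 per patient-year.

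- True first-event probability: 1 − exp(−1) = 63.2%, or 60 × 0.632 = 37.9 first events.
- If a fraction q of first events is recorded as loss at the event time, Kaplan-Meier estimates 1 − exp(−(1 − q)).

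| q (assumed) | Estimate | Points too low |
|---|---|---|
| 5% | 61.3% | 1.9 |
| 10% | 59.3% | 3.9 |
| 20% | 55.1% | 8.1 |
| 30% | 50.3% | 12.9 |

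If every hidden event in step 2 were a first event, q would run from 0.75/37.9 = 2.0% to 4.5/37.9 = 11.9%. The estimate would then be about 0.7 to 4.6 points too low. The 20% and 30% rows need heavier loss than step 2 assumes. If loss is unrelated to events and censoring is at the last ascertainment date, there is no bias.

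**4. Effect of unascertained time.** Suppose lost subjects leave on average at 6 months and then gain 14 to 90 days of event-free time from later transmissions (assumed).

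- 5% lost, 14 days: person-years 60 − 3 × 0.5 = 58.5; added 3 × 14/365.25 = 0.115; rate 58.5/58.615 = 0.998.
- 15% lost, 90 days: person-years 60 − 9 × 0.5 = 55.5; added 9 × 90/365.25 = 2.218; rate 55.5/57.718 = 0.962.

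Against a true rate of 1, the dilution is about 0.2% to 4%.

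**5. Which analyses are touched.** The primary analysis plots daily sensor averages around adjudicated events and involves no censoring. CIP 14.6 and SAP 7.4 admit an event only if device data exist before and after onset. A recovered event therefore helps the plots only where those data were transmitted. CIP 10.11 warns that RAMware data are overwritten if not sent manually within 32 days.

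**The case against.** The strongest reply is that 10.23.3 states what must be documented once loss has been determined. It is a floor, with IRB/EC rules added, and does not say that two attempts suffice for exit. Other text favours retention. CIP 10.3 keeps the visit schedule after a missed visit and prefers a late visit to none. CIP 10.23.6 offers reduced data collection instead of exit. Adverse events are to be reported as they occur (CIP 10.2, 10.6) and collected at exit, death is a separate exit reason, and sites must try to retrieve information on deaths elsewhere (CIP 12.6). Sites also receive a report of missed manual transmissions (CIP 10.11).

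Much of this stands, and it rules out several stronger readings that a reader might infer:

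- **That the plan directs admissions and deaths to be recorded as loss.** It does not. A known death must be reported, and SAP 7.1.1 gives deaths and exits separate categories in the STROBE diagram. Only undiscovered events could be misplaced.
- **That lost subjects are carried event-free to 12 months.** They are censored at the latest of three dates. A subject with an earlier COPD event is unaffected in the first-event analysis.
- **That the primary plots lose their severe events because of this rule.** Often the surrounding sensor data would be missing anyway.
- **That losses among 100 enrolled subjects can be divided by 60 events.** The 60 events come from 60 subjects, so the bases must match.

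What does not stand is that the safeguards close the gap. The death duty begins with the investigator's knowledge, and collecting events at exit depends on reaching the subject or looking elsewhere. Nothing in 10.23.3 requires anyone to look.

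**Conclusion.** The point holds as a gap in ascertainment and in the choice of censoring date. A site can follow the CIP as written and still miss COPD events and deaths between the last completed call and exit, although it has access to a source that might show them.

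On assumed inputs (5–15% lost, 25–50% of those hiding an event), the ceiling is 0.75–4.5 of 60 expected COPD events, about 1.3–7.5%. The matching understatement of the exploratory 12-month first-event estimate is about 0.7–4.6 points under a constant rate. The documents supply no loss rate to narrow this.

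The study is exploratory with no hypothesis, so no formal conclusion is at risk. The change is still worth making, because the study exists to link sensor data to events and the remedy is cheap. One matter remains outside it: SAP 7.9.3 has no separate rule for a known death without a COPD event, and a record check does not settle that.

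**What to change.** **CIP 10.23.3.** Before the exit form is completed for loss to follow-up, require a documented review, within consent, of the accessible medical record, vital status and CareLink transmission status. It should cover the period from the last completed contact to the exit date. Any qualifying adverse event or death found is entered and sent for EAC review. Because the review precedes exit, it is compatible with 10.23.1.

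**SAP 7.9.3.** Censor at the last date on which COPD events were actually ascertained: the last completed adverse-event contact or, if later, the date of the last record entry reviewed. Do not use a later device transmission. Do not use the date of the search itself either, which would credit event-free time that the record may not cover. Report the reasons for loss.

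**Cost.** About one sentence in each document and a short chart review for a few subjects. Care given outside the site's system may still be missed.

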## 10.23.4 Subject Chooses to Exit (i.e. Revokes Consent)

A subject can withdraw from the study at any time. If the subject wishes to exit from the study (i.e. the subject revokes consent), the study site is required to document the reason for exit on the Exit CRF. In addition, study sites shall follow the regulations set forth by the governing EC. If possible, the following data should be collected prior to subject withdrawal:

- Reason for exit

## 10.23.5 Investigator Withdraws Subject

No subjects should be withdrawn by investigators unless compelling medical justification is present. It is recommended investigators discuss any withdrawals with the study team prior to withdrawing subjects. If an Investigator Withdrawal is necessary, the following data should be collected prior to subject withdrawal if possible:

- Reason for subject withdrawal

## 10.23.6 Conditional Disengagement

After a subject is enrolled/randomized every effort should be made to keep the subject in the study. However, it is recognized that there are circumstances where limited data may be collected, or study exit will need to occur. In these cases we will consider either modified data collection requirements where subjects may conditionally disengage in study procedures but data from the subject can still be

collected because the subject has not revoked consent, or exit when study participation is completely ended. In randomized subjects, modified data collection is always preferred over exit.

Subjects may be conditionally disengaged from study procedures for any of the following reasons:

- Subject chooses to disengage (e.g., follow-up schedule cannot be adhered to, study burden too large, relocation to another geographic location but telephone follow-up still acceptable)
- Investigator deems conditional disengagement necessary (e.g. medically justified)

If the subject wishes to disengage from the study, or the investigator deems it necessary, the study site is required to document the reason. Prior approval from the study team is required and a Limited Data Collection CRF needs to be completed. Data collection requirements no longer apply, but study sites are encouraged to collect as much data as possible on the regular CRFs.

